**3.4.10 Completed Subjects**

A Completed Subject is an ITT Subject who completes the Month 12 Assessment either in-person or remotely. The date on which the Month 12 Assessment is completed is the Completed Subject's Exit Date and a Study Exit CRF will be completed. No study data on events with an onset date after the Exit Date may be collected or included as part of the study database or analyses.

**3.4.11 Incomplete Subjects**

An Incomplete Subject is any ITT Subject who does not become a Completed Subject. Anticipated reasons for failure to become Completed Subjects include withdrawal of consent by a subject, death or incapacity of a subject, lost-to-follow-up (LTFU) status and termination by the Investigator.

A LTFU Subject is an ITT Subject who ceases to participate in study follow-up procedures or who fails to respond to contact attempts. The Investigator will attempt to contact such a subject 2 or more times within 60 days and if there is no return to study participation, the subject will be deemed LTFU. The Investigator will document that a minimum of two attempts were made to contact the subject, including sending a certified letter if current address is known, prior to terminating the subject from the study.

The date on which a subject is determined to be an Incomplete Subject is their Exit Date, and a Study Exit CRF will be completed including the reason for becoming an Incomplete Subject.

No study data on events with an onset date after the Exit Date may be collected or included as part of the study database or analyses. However, if an Incomplete Subject's exit is due to an AE, the Investigator should, if subject consent is documented, follow the subject until the AE has resolved or is considered stable, but in any case, not more than 390 days have passed since the Index / Rescheduled Index Procedure. The data related to that AE may be collected and included in the study database and analyses under such consent.

[figure not shown]
### 3.4.12 Per Protocol Subjects

A Per Protocol (PP) Subject is a Safety or ITT Subject without major protocol deviations that would affect the completeness, accuracy and reliability of the study data. Major protocol deviations that exclude subjects from a PP Population are the following:

- Failure to meet any of the following study entry criteria:
  - Arrhythmia different than PAF (Inclusion Criterion 1)
  - Prior cardiovascular procedures, implants or conditions (Exclusion Criteria 3 and 4)
  - Medical conditions (Exclusion Criterion 11)
- Failure to receive the randomized ablation treatment for PVI as specified in this protocol (**Section 5.2 or Section 5.3**)
- Receipt of a prohibited study drug (amiodarone, except intra-procedurally to control an arrhythmia )
- In addition, the data of Severe COVID-19 Subjects will be censored beginning on the Onset Date of infection.

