### **3.3.2 Exclusion Criteria**

Patients will be excluded from participating in this study if they meet any one of the following exclusion criteria:

- 1. AF that is any of the following:
  - a. Persistent (both early and longstanding) by diagnosis or continuous duration  $> 7$  days
  - b. Requires four (4) or more direct-current cardioversions in the preceding 12 months
  - c. Secondary to electrolyte imbalance, thyroid disease, alcohol or other reversible / non-cardiac causes
- 2. Any of the following atrial conditions:
  - a. Left atrial anteroposterior diameter  $\geq 5.5$  cm (by MRI, CT or TTE)
  - b. Any prior atrial endocardial or epicardial ablation procedure, other than right sided cavotricuspid isthmus ablation or for right sided SVT
  - c. Any prior atrial surgery
  - d. Intra-atrial septal patch or interatrial shunt
  - e. Atrial myxoma
  - f. Current LA thrombus
  - g. LA appendage closure, device or occlusion, past or anticipated
  - h. Any PV abnormality, stenosis or stenting (common and middle PVs are admissible)
- 3. At any time, one (1) or more of the following cardiovascular procedures, implants or conditions:
  - a. Sustained ventricular tachycardia or any ventricular fibrillation
  - b. Hemodynamically significant valvular disease:
    - i. Valvular disease that is symptomatic
    - ii. Valvular disease causing or exacerbating congestive heart failure
    - iii. Aortic stenosis: if already characterized, valve area  $< 1.5$ cm or gradient  $> 20$  mm Hg
    - iv. Mitral stenosis: if already characterized, valve area  $< 1.5$ cm or gradient  $> 5$  mm Hg
    - v. Aortic or mitral regurgitation associated with abnormal LV function or hemodynamic measurements
  - c. Hypertrophic cardiomyopathy
  - d. Any prosthetic heart valve, ring or repair including balloon aortic valvuloplasty

- e. Pacemaker, implantable cardioverter defibrillator or cardiac resynchronization therapy devices
- f. Any IVC filter, known inability to obtain vascular access or other contraindication to femoral access
- g. History of rheumatic fever
- h. History of congenital heart disease with any residual anatomic or conduction abnormality
- 4. Any of the following procedures, implants or conditions:
  - a. At baseline:
    - i. New York Heart Association (NYHA) Class III or IV
    - ii. LVEF < 40%
    - iii. Symptomatic hypotension
    - iv. Uncontrolled hypertension (SBP > 160 mmHg or DBP > 95 mmHg on two (2) BP measurements at baseline assessment)

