4.1.12 Per Protocol Subjects

Per Protocol (PP) Subjects are all Subjects without major protocol deviations that would affect the completeness, accuracy and reliability of the study data. Major protocol deviations¹ that exclude subjects from the PP Population are the following:

- Failure to meet any of the following study entry criteria:
 - Arrhythmia different than PAF (Inclusion Criterion 1)
 - Prior cardiovascular procedures, implants or conditions (Exclusion Criteria 3, 4)
 - Medical conditions (Exclusion Criterion 11)
- Failure to receive the randomized ablation treatment for PVI as specified in Protocol Section 5.2 and Protocol Section 5.3.
- Receipt of a prohibited study drug (amiodarone)
- In addition, the data of Severe COVID-19 Subjects will be censored beginning on the Onset Date of infection.

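### The Per Protocol list leaves out Exclusion 2 and Exclusions 1b and 1c, so the PP checks on the two non-inferiority tests can keep subjects with ineligible atria or veins

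*Protocol*

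**What the plan says.** Protocol 3.4.12 defines PP subjects as those free of major deviations that would harm the completeness, accuracy or reliability of the data. It then states which deviations count, those "that exclude subjects from a PP Population are the following". Three entries concern eligibility:

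- "Arrhythmia different than PAF (Inclusion Criterion 1")
- "Prior cardiovascular procedures, implants or conditions (Exclusion Criteria 3 and 4")
- "Medical conditions (Exclusion Criterion 11")

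The remaining entries are failure to receive the randomized PVI treatment, receipt of amiodarone, and censoring of data from Severe COVID-19 subjects. SAP 4.1.12 names the same criteria, for example "Prior cardiovascular procedures, implants or conditions (Exclusion Criteria 3, 4").

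Exclusion 2 in Protocol 3.3.2 holds the atrial and vein criteria. They include:

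- 2a: "Left atrial anteroposterior diameter" of 5.5 cm or more
- 2b: "Any prior atrial endocardial or epicardial ablation procedure, other than right sided cavotricuspid isthmus ablation or for right sided SVT"
- 2g: closure or occlusion of the left atrial appendage
- 2h: "Any PV abnormality, stenosis or stenting (common and middle PVs are admissible")

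Exclusion 1 covers persistent AF (1a), four or more cardioversions in 12 months (1b), and AF from reversible or non-cardiac causes (1c).

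Protocol 3.7 keeps a subject in the study when an eligibility criterion is later found to have been misjudged. Protocol 9.5, 9.6 and 9.10 make PP a sensitivity analysis for primary safety, primary effectiveness and superiority. Protocol 9.9 makes it a supplemental analysis for PV cross-sectional area.

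**The concern.** The omitted criteria lie close to the endpoints. Treatment Success depends on arrhythmia recurrence. Pulmonary vein stenosis and the PV-area endpoint are both measured against the baseline scan. Read literally, the list removes a subject with a BMI of 40.5 (11a) or a gastrointestinal bleed 80 days before consent (4b), but keeps one with a previous left atrial ablation or a stented vein. That sits badly with the section's own aim of protecting the reliability of the data. Neither document gives a reason for the selection; the footnote to the list explains only why consent, confidentiality and subject-rights deviations are left out.

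In a non-inferiority trial, ineligible subjects who fare alike in both arms pull the observed difference toward zero, which makes non-inferiority easier to show. PP is the planned analysis that would be expected to guard against this.

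**Working it through.** **1. Criteria against the PP list.**

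| Criterion | Caught by the PP list? |
|---|---|
| 1a persistent AF | Yes, in effect: it mirrors Inclusion 1a |
| 1b four or more cardioversions | No |
| 1c reversible or secondary AF | Partly: Exclusion 11 has open wording and names active alcohol abuse |
| 2a enlarged left atrium | Not named |
| 2b prior atrial ablation | No |
| 2c prior atrial surgery | Only if heart surgery within 6 months (4c) |
| 2d septal patch or shunt | Possibly, through congenital disease (3h) |
| 2e atrial myxoma | Not named |
| 2f left atrial thrombus | Handled procedurally in Protocol 5.2 and 5.3 |
| 2g appendage closure | No |
| 2h PV abnormality, stenosis or stenting | Not named |

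Inclusion 2 and 3 and Exclusions 5 to 10 and 12 to 14 are also unlisted. This point does not extend to them.

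**2. Other routes out of the analysis.** Protocol 3.7 keeps misjudged subjects enrolled. SAP 16.1 to 16.3 cover missing data, the imputation model, COVID-19, extra ablation at the index procedure, PP itself and Kaplan-Meier estimates. None removes a subject for breaching Exclusion 1b or 2.

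**3. Illustration for effectiveness.** The plan has no figure to reproduce here. The sketch assumes a fixed sample and a normal approximation.

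Inputs from the SAP:
- threshold 0.956 (9.1), so z = 1.706
- margin 0.15, with true rates at the margin of 0.50 against 0.65 (14)
- 225 per arm (450/2) and 375 per arm (750/2)

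Assumed, with no source in the documents: an ineligible share π of 0, 2% or 5% in each arm, with success 0.40 in both arms.

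Formulas:
- p_T = 0.50(1 − π) + 0.40π and p_C = 0.65(1 − π) + 0.40π
- difference = −0.15(1 − π), so the shift from the margin is 0.15π
- SE = √{[p_T(1 − p_T) + p_C(1 − p_C)]/n}
- chance of crossing the threshold = 1 − Φ(1.706 − shift/SE)

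Worked case, π = 5% and n = 225: p_T = 0.495, p_C = 0.6375, difference −0.1425, shift 0.0075. SE = √(0.48107/225) = 0.0462, and shift/SE = 0.162. Then 1 − Φ(1.544) = 6.1%.

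| Per arm | π = 0 | π = 2% | π = 5% |
|---|---|---|---|
| 225 | 4.4% | 5.0% | 6.1% |
| 375 | 4.4% | 5.2% | 6.7% |

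The 4.4% is simply 1 − 0.956 for a fixed sample. It is not comparable with the 0.0487 that SAP 14 simulates for the adaptive design. If ineligible subjects also differed by −0.15 between arms, the shift would be zero and every entry would stay at 4.4%. No corresponding calculation was made for safety.

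**The case against.** The strongest reply is that PP decides nothing. Study success rests on the MITT and Safety analyses (SAP 4.2 and 6), and no PP threshold is set. That stands: applying 0.956 to PP only illustrates the direction and rough size of the effect.

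Second, Exclusion 11 is open-ended and includes conditions that could alter outcome data, so part of 1c, and arguably vein stenosis or a large atrium, might be read into it. This stands in part for 1c. It is a weak basis for 2a and 2h, which have their own criterion, and it hardly reaches a past ablation or a cardioversion count. The phrase about prior cardiovascular procedures might seem to cover ablation, but the list ties it to Exclusions 3 and 4.

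Third, baseline echocardiography and cardiac CT or MRI are required (Protocol 4.7.1), and eligibility data are fully source-verified (Protocol 11.3). Such subjects should be few.

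Stronger readings are tempting but unsupported:

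- A reader might infer that persistent AF slips through. It does not, because Inclusion 1 catches it.
- A reader might infer that a subject with no failed drug (Inclusion 1c) stays in PP because of the label about arrhythmia type. The list cites Inclusion Criterion 1 as a whole, and 1c is part of it.
- A reader might infer that all four formal tests are exposed. Dilution toward no difference makes superiority and the PV-area test harder to pass, so for those two it is conservative.

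**Conclusion.** The omission is a matter of text and is certain: neither document names Exclusion 1 or 2. Its practical reach is Exclusion 2 (notably 2a, 2b, 2g and 2h), 1b, and the part of 1c that Exclusion 11 does not cover. The consequence is confined to the PP sensitivity analyses of the two non-inferiority tests, which can be diluted toward no difference.

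The size cannot be stated, because the documents give no expected number of such subjects. The illustrative rise from 4.4% to between 5.0% and 6.7% depends on the assumed 2% to 5% share, and on the further assumption that ineligible subjects do equally poorly in both arms. A reader might infer that the trial's own type I error is inflated. The documents do not support that, since PP carries no decision rule. This is a minor point and a cheap improvement.

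**What to change.** In Protocol 3.4.12 and SAP 4.1.12, replace the eligibility entries with: failure of Inclusion Criterion 1 (any of 1a, 1b or 1c), or of Exclusion Criteria 1, 2, 3, 4 or 11. Drop the label about arrhythmia type, so that the criterion number governs. Add one exception: left atrial thrombus (2f) managed by rescheduling under Protocol 5.3 does not remove a subject from PP. Without it, the new list would conflict with Section 5.3, which permits rescheduling, and with the PP list's own acceptance of treatment under that section. If the sponsor prefers the present selection, it should state why.

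The cost is one line in each document and a slightly smaller PP set, with a small loss of precision. No new data are needed.

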**Pulsed Field Subjects:**

The use of ICE is required for Pulsed Field Ablation procedures.

The FARADRIVE Steerable Sheath will be prepared and advanced via guidewire to the LA.

Esophageal temperature monitoring, esophageal cooling and esophageal deviation are unnecessary during ablation with the FARAWAVE Pulsed Field Ablation Catheter and should not be utilized.

The FARAWAVE Pulsed Field Ablation Catheter will then be prepared and advanced to the LA through the FARADRIVE Steerable Sheath. After confirming an ACT of 300 or greater, ablation of the PVs to achieve isolation will be performed according to the approved IFU documents and institutional practice.

Ablation will be attempted in every clinically relevant PV, including any vein with an active muscular sleeve. Small anomalous PVs that are electrically silent need not be attempted.

PVI ablation may be repeated at the Investigator's discretion. Each addressable PV will be ablated in turn. The isolating effect of the PVI ablation(s) will be checked periodically and then finally twenty (20) minutes after the last PVI ablation. Adenosine may be used for the final assessment but is not required.

At the conclusion of the PVI ablation procedure, the FARAWAVE Pulsed Field Ablation Catheter will be undeployed and withdrawn from the FARADRIVE Steerable Sheath.

The functional status of both phrenic nerves will be assessed before the study is concluded.

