#### 6.3.2 Acute Procedural Failure

The absence of Acute Procedural Success, including the use of any non-randomized energy modality for PVI.

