### **9.5 Assessment of the Primary Safety Endpoint**

The primary safety endpoint for this study is the CSE defined in Protocol **Section 7.1**.

The principal analysis population for the safety endpoints is the Safety Population. Analysis in the PP Population will also be conducted as a sensitivity analysis.

The analysis of the primary safety endpoint is a test of non-inferiority of the event rate at 12 months using a non-inferiority margin of 8%. The null and alternative hypotheses are presented below for primary safety:

$$H_0: Q_T \geq Q_C + 0.08 \text{ versus } H_A: Q_T < Q_C + 0.08$$

where  $Q_T$  is the CSE proportion in the Pulsed Field (Treatment) Group and  $Q_C$  is the CSE proportion in the Thermal (Control) Group. The differences in the proportion of subjects with 1 or more CSE events between the Pulsed Field Group and the Thermal Group will be tested with a Bayesian statistical method and the prior distributions for  $Q_T$  and  $Q_C$  in these calculations are Beta (0.5, 0.5), which is the Jeffreys non-informative prior.  $Q_T$  will be deemed to be non-inferior to  $Q_C$  if it can be established that the posterior probability  $Pr(H_A | \text{data}) > \Psi_{\text{saf}}$ , where  $\Psi_{\text{saf}}$  is a pre-specified threshold value that controls the one-sided type I error rate (under simulation) at level 0.05. In the absence of missing data, the posterior distributions for  $Q_T$  and  $Q_C$  would be conjugate Beta distributions. However, some missing data are expected. Therefore, Bayesian multiple imputation of 12-month outcomes will be employed in the principal analysis. The imputation model accounts for primary outcome information up through the time of censoring. Details on the modeling for this imputation are given in the SAP.

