16.3 Other Sensitivity Analyses

- A sensitivity analysis of the Primary Effectiveness Endpoint will also be conducted, in which subjects requiring ablation for an accessory pathway, AVNRT, treatment-emergent left AFL, or incessant AT are counted as treatment failures.
- As indicated in Section 9, the primary analysis for effectiveness will be conducted in the mITT population, but supportive analyses will also be conducted in the PP population. Similarly, as indicated in Section 10, the primary analysis for safety will be conducted in the Safety Population, supportive analyses will also be conducted in the PP population.
- For the primary effectiveness endpoint, Kaplan-Meier estimates of event rates will also be presented.

17 Heterogeneity/Poolability

Incidence of the primary safety and primary effectiveness endpoints will be evaluated for poolability across key subgroups. In particular, the primary endpoints will be examined for differences between sexes and sites. A specific categorization of sites is those that use RF as the control therapy and those that use cryoablation as the control therapy. Poolability of treatment effect over this factor (site uses RF, site uses cryo) will also be studied.

Poolability tests will be conducted with frequentist methods. For each factor of interest (sex, site), a logistic regression will be fit, with predictors Treatment Group, the factor, and their interaction. If the interaction p-value is significant at the level 0.15, further analyses will be conducted. At a minimum, any baseline variables found to differ between treatment groups and any baseline variables found to significantly predict a primary event (Treatment Response, or occurrence of CSE) in univariate analyses will be candidates for inclusion in logistic regression adjustment to see whether the apparent heterogeneity is explained by these factors. If so, analyses that adjust for these factors will be presented. If not, further analyses will be conducted, including presenting results separately by sex / site.

Sites with fewer than 8 subjects will be considered small sites. Poolability analyses will be summarized descriptively for all sites, but inferential tests of poolability across sites will exclude small sites. If there are many small sites, or many sites with 0 events, inferential tests of poolability across sites may not be conducted.

18 Other Planned Analyses

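### The one Per Protocol exclusion list also governs the supportive safety analysis, so PP safety membership can depend on the complication being counted

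*Protocol*

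**What the plan says.** Protocol 3.4.12 builds the PP set from either base population: "A Per Protocol (PP) Subject is a Safety or ITT Subject without major protocol deviations that would affect the completeness, accuracy and reliability". One list of disqualifying deviations follows, and it is not split by endpoint. Among them is "Failure to receive the randomized ablation treatment for PVI as specified in this protocol", with a reference to Sections 5.2 and 5.3. SAP 4.1.12 repeats it: "Failure to receive the randomized ablation treatment for PVI as specified in Protocol Section 5.2 and Protocol Section 5.3".

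Section 5.2 sets out what the treatment consists of. For Pulsed Field Subjects, "Ablation will be attempted in every clinically relevant PV, including any vein with an active muscular sleeve", with isolation checked a last time 20 minutes after the final PVI lesion. Thermal Subjects have the same requirement. Section 6.3.2 classes conversion as a failure of the acute procedure: "The absence of Acute Procedural Success, including the use of any non-randomized energy modality for PVI".

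Protocol 9.5 gives the role of PP for the CSE: "The principal analysis population for the safety endpoints is the Safety Population. Analysis in the PP Population will also be conducted as a sensitivity analysis". SAP 16.3 says the same: "the primary analysis for safety will be conducted in the Safety Population, supportive analyses will also be conducted in the PP population". Neither document exempts a case that was cut short or converted because of an adverse event. The emergency-deviation clause in Protocol 12.13 deals with approval and notification, not with PP membership.

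**The concern.** Most CSE components count only with onset within 7 days of the procedure, and several (tamponade or perforation, stroke, myocardial infarction, death) can arise during it. If such an event ends the case before every relevant vein has been attempted, or leads to a non-randomized catheter, the plain wording takes the subject and the event out of the PP safety set. Membership then depends on the outcome under analysis.

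The Safety Population avoids this by requiring only catheter insertion (Protocol 3.4.8). The PP list gives up that protection in the one alternative population planned for the CSE. At stake is how the PP safety result can be read: agreement with the principal result may be partly built in, and disagreement would be hard to interpret.

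**Working it through.** **Plan's own figure.** Protocol 9.7 and SAP 11.1 give 214 per group for safety (CSE 0.08 in both, margin 0.08, one-sided alpha 0.05, 90% power, Farrington-Manning). With restricted null estimates 0.1353 and 0.0553:

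- s0 = √(0.1353×0.8647 + 0.0553×0.9447) = 0.4114
- s1 = √(2×0.08×0.92) = 0.3837
- n = [(1.645×0.4114 + 1.282×0.3837)/0.08]² = 213.3, so 214 per group and 428 in total, as stated. 428/0.95 = 450.5; the plan says 450.

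**Inputs from the documents.** True CSE rates of 16% v 8% (the SAP 14 null), margin 0.08, Beta(0.5, 0.5) priors, posterior threshold 0.966 (SAP 10.1).

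**Assumed.** The share f of CSE subjects whose complication stopped or converted the ablation. The documents do not give it, so a range is shown. Other PP exclusions are ignored, data are complete and N is fixed.

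**PP rate.** Removing a share f of an arm's CSE subjects from numerator and denominator gives Q(1−f)/(1−Qf). At 225 per arm and f = 10%, Pulsed Field goes from 36/225 to 32.4/221.4 = 14.6%, and Thermal from 18/225 to 16.2/223.2 = 7.3%.

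| Share lost, Pulsed Field / Thermal | PP rates | PP difference | Chance PP meets the criterion, N=450 |
|---|---|---|---|
| 0 / 0 | 16.0% v 8.0% | 8.0 points | 0.036 |
| 10% / 10% | 14.6% v 7.3% | 7.4 | 0.056 |
| 25% / 25% | 12.5% v 6.1% | 6.4 | 0.115 |
| 50% / 50% | 8.7% v 4.2% | 4.5 | 0.37 |
| 15% / 30% | 13.9% v 5.7% | 8.2 | 0.032 |

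The last column is an exact enumeration at 225 per arm, without interim looks or missing data. Its 0.036 in the first row is therefore not the SAP's simulated 0.0528 for the adaptive design. The 50% row is only an outer illustration.

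**Where the direction turns.** Take f = 10% in Pulsed Field, so its PP rate is 0.1463. For the difference to stay at 0.08 the Thermal PP rate must be p = 0.0663. Solving for the Thermal share, f = (0.08−p)/[0.08(1−p)] = 0.0137/0.0747 = 0.183, about 1.8 times the Pulsed Field share. The same calculation gives about 1.5 times for a true 13% v 8% and 1.2 times for 10% v 8%. Beyond those ratios PP enlarges the excess.

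**Does this raise the chance of a false claim?** The two analyses were simulated on the same data at 16% v 8%, 225 per arm, with equal shares lost. The Safety Population test and the PP test both passed in 3.4% of trials at f = 0 and in 3.2% at f = 10%, 25% and 50%. The extra PP passes come almost entirely from trials in which the principal test had already failed.

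**The case against.** The strongest reply is that nothing is decided in PP. Every stopped or converted case with a catheter inserted stays in the Safety Population by randomized assignment, and SAP 6 bases success on the primary tests. A reader might infer from the rising PP pass probabilities that the plan makes a false safety claim more likely. It does not: those probabilities are unconditional, and the joint pass rate does not rise. This stands.

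Second, a reader might infer that PP always hides an excess. That fails once Thermal loses a sufficiently larger share, and the documents do not say which pattern to expect.

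Third, a high f has no support in the documents. Many CSE components would not usually end an ablation (vascular access complications, pericarditis, stenosis, fistula). Acute success in the feasibility studies was 40/40, 71/71 and 10/10 (Protocol 1.4), including the subject with peri-procedural tamponade. This points to a low f. It is thin evidence, however: only three subjects had a primary safety event (1, 2 and 0), one of those after a remapping procedure, and nothing is shown for the Thermal technologies.

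Fourth, whether a complication-stopped case counts as failing to receive treatment is not stated outright. That is fair. The reading above is the plain one, but it remains an interpretation, and a sentence in the plan would settle it.

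Fifth, one might argue that the amiodarone exclusion biases PP safety in the same way. The documents do not support this: Protocol 3.4.12 exempts intra-procedural use for an arrhythmia, and nothing links later use to the CSE. What does stand is that SAP 4.1.12 omits that exemption.

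Other planned analyses (completers-only, tipping point, COVID-19, related SAEs) add context, but none addresses exclusion caused by the event itself.

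**Conclusion.** The point holds in a limited form. One PP exclusion list serves both endpoints, and on its plain wording it can remove subjects from the supportive CSE analysis because they had a CSE. The principal safety test and the study success rule are untouched.

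With equal loss in the two arms, or more in Pulsed Field, a true excess shrinks: by 0.6 points at an assumed 10% share and 1.6 points at 25%, for 16% v 8%. It grows if Thermal loses about 1.8 times the Pulsed Field share or more. The size rests on an undocumented share that the feasibility data suggest is low, and the finding rests on the plain reading of the exclusion. This is a cheap improvement to a supportive analysis, not a flaw in the trial's inference.

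**What to change.** In Protocol 3.4.12 and SAP 4.1.12:

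- State that, for the PP analysis of the CSE, a procedure stopped, shortened or converted because of an adverse event does not exclude the subject.
- State that PP safety is analysed by randomized group.
- Add a listing of PP exclusions by arm, with the reason and CSE status.
- Reconcile the amiodarone exclusion in SAP 4.1.12 with the intra-procedural exception in Protocol 3.4.12. The SAP itself says that unmarked differences from the Protocol are inadvertent.

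The cost is a few sentences, one population flag and one listing. The primary tests, sample size, trial conduct and PP effectiveness set do not change. The small downside is that the PP safety set moves closer to the Safety Population and so offers less contrast with it.
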